6.2.4. Multiple Comparisons/Multiplicity

Since there are no formal hypothesis tests in this study, no adjustment for multiplicity will be made.

6.2.6. Missing, Unused, and Spurious Data

Binary endpoints / Continuous data:

Missing data are assumed to be missing at random and ignorable. Missing data will not be estimated or imputed. Denominators for percentages will be based only on the number of subjects with non-missing values.

The only exception are some derived Day 1 to Day 7 endpoints for solicited AEs. Additional details for handling of missing data in these cases can be found in Section 6.5.1.1.

Dates:

For partial or missing AE start dates the following imputation rules will be applied:

1. If year is not missing and is after the year of first dose:
 - a. If month is missing, then month will be imputed as January.
 - b. If day is missing, then day will be imputed as the first of the month.
2. If year is not missing and is the same as the year of the first dose:
 - a. If month is missing, then impute the month as the month of the first dose date.
 - b. If day is missing, and the month is the same as the month of the first dose date, then impute day as the day of the first dose date.
 - c. If day is missing but month is after the month of first dose date, then impute day as the first day of the month.
3. If year is missing, then impute the year as the year of the first dose date:
 - a. If month is missing, then impute the month as the month of the first dose date.
 - b. If day is missing, then impute the day as the day of the first dose date.
4. If the start date is completely missing, but the AE is either ongoing (i.e. AE stop date is missing) or the stop date is after the first dose date then impute the start date as the first dose date.
5. For any cases involving the rules above, if the AE end date is before the AE start date, then do not impute the AE start date and assume that the AE is treatment emergent/concomitant for the purpose of the analysis. Further, if the AE stop date occurs prior to the first dose date, do not impute the AE start date, and assume that the AE is not treatment emergent.

No imputations will be applied to AE stop dates or other dates. As indicated above, AEs with missing stop date are considered ongoing.

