## **8.5 Reporting of Adverse Events**

### **8.5.1 Reporting Periods**

The reporting period for solicited AE begins immediately after study vaccine administration and continues for 7 days after the injection. The reporting period for unsolicited AE is immediately after study vaccine administration on Day 1, continuing through Month 1. AE that correspond to solicited AE terms but occur outside of (or continue past) the solicited AE collection periods are also collected through the unsolicited AE reporting periods. The reporting period for SAE begins at the time of informed consent and continues for the duration of study participation. A summary of the reporting periods is presented in [Figure 3](#).

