1. INTRODUCTION AND OBJECTIVES OF ANALYSIS

1.1. Introduction

This statistical analysis plan (SAP) is designed to outline the methods to be used in the analysis of study data to answer the study objective(s). Analysis sets, data handling rules, statistical methods, and formats for data presentation are provided. The statistical analyses and summary tabulations described in this SAP will provide the basis for the results sections of the CSR for this trial.

Analyses planned for the Data Monitoring Committee (DMC) meeting at the end of Stage 1 were described in the separate document “VAX31-101 DMC Charter v1.0” dated 31-OCT-2023.

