6.5.1.2. Unsolicited Adverse Events

An unsolicited AE is an AE that is spontaneously reported by the subject or discovered by the Investigator. SAEs, NOCIs and MAAEs would be recorded as part of the collection of unsolicited AEs as specified in the visit procedures. Unsolicited AEs are collected separately from solicited AEs.

Solicited AEs continuing beyond 7 days will be identified using rules given in Section 5.2. They will not be presented in the summaries of unsolicited Adverse Events, but only in a Listing.

The definition of a treatment emergent AE (TEAE) is an event that occurs after vaccination and within the 30 days after vaccination (i.e., excluding those after a subject has given informed consent, but before vaccination):

- Onset (days) = Start date of AE – Date of Study Vaccine Administration + 1
- An AE is a TEAE if Onset \geq 1 and Onset \leq 30 and is not a continuing solicited AE

Adverse events are summarized by subject, therefore, in any tabulation, a subject contributes only once to the count for a given adverse event (SOC or preferred term).

Unsolicited AEs will be coded using the Medical Dictionary for Regulatory Activities (MedDRA) and will be summarized by decreasing frequency of SOC and preferred term within SOC in the control group, as follows:

- Unsolicited TEAEs
- Possibly or probably related unsolicited TEAEs
- Unsolicited TEAEs leading to study withdrawal

- SAEs
- Possibly or probably related SAEs
- NOCIs
- Possibly or probably related NOCIs
- MAAEs
- Possibly or probably related MAAEs
- AEs leading to death (only presented on the Safety Population overall)

Following summaries will be presented on the Safety Population overall only by decreasing frequency of PT, with an additional column “VAX-31” combining all subjects vaccinated with any dose of VAX-31:

- Unsolicited TEAEs
- Possibly or probably related unsolicited TEAEs

Following by-subject Listings will be provided:

- Pre-vaccination AEs (non-emergent)
- All unsolicited TEAEs
- All Serious post-vaccination AEs, NOCIs and MAAEs

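### SAP 6.2.6 rule 3 assigns the dose year to an AE start date with a known month and no year, which puts a post-vaccination event before vaccination when follow-up crosses a year end

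*SAP*

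**What the plan says.** SAP 6.2.6 sets out five rules for partial or missing AE start dates.

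- **Rule 3**: "If year is missing, then impute the year as the year of the first dose date". Its sub-rules are 3a, "If month is missing, then impute the month as the month of the first dose date", and 3b, "If day is missing, then impute the day as the day of the first dose date". A month or day that was recorded is left as it is.
- **Rule 4** covers only a start date that is completely missing, and sends it to the dose date if the event is ongoing or stops after the dose.
- **Rule 5** has two parts. First, when the stop date precedes the start date, the start is left unimputed and the event is classed as emergent. Second, if the stop date is before the first dose, the start is not imputed and the event is not treatment emergent.

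SAP 6.5.1.2 defines Onset as start date minus vaccination date plus 1, and a TEAE as Onset 1 to 30, excluding continuing solicited AEs. It also plans a listing of pre-vaccination AEs. On collection, Protocol 8.5.1 states: "The reporting period for unsolicited AE is immediately after study vaccine administration on Day 1, continuing through Month 1". The same section starts SAE reporting at informed consent. SAE, NOCI and MAAE percentages within 6 months are primary endpoints (SAP 3.2), and follow-up runs to 180 days (Protocol 4.3).

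**The concern.** An imputation rule for AE start dates should not move an event that happened after vaccination to a date before it. Rule 3 does so whenever the event falls in the calendar year after the dose and the record has a month but no year. The endpoint directly exposed is the primary percentage with unsolicited AEs within 1 month. The 6-month SAE, NOCI and MAAE percentages are exposed only if onset date is used to select events for them. For non-serious unsolicited AEs a pre-dose date cannot be right, because collection begins only after the injection. For events after vaccination the misdating can only lower the count.

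**Working it through.** The plan gives no figure for this rule, so there is none to reproduce. The check applies the rules to the calendar.

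**Inputs.** Rules 3 to 5 (SAP 6.2.6); the Onset formula and the 1 to 30 window (SAP 6.5.1.2); 180 days of follow-up (Protocol 4.3). Vaccination dates are assumed, because the documents do not give them. The only calendar clue is that the analyses for the Stage 1 DMC meeting "were described in the separate document “VAX31-101 DMC Charter v1.0” dated 31-OCT-2023".

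**Worked record.** Dose 15 December 2023; AE start 8 January, year missing; stop 12 January 2024.
- True start 8 January 2024, 24 days after the dose: Onset = 24 + 1 = 25, a TEAE.
- Rule 3 start 8 January 2023, 341 days before the dose: Onset = -341 + 1 = -340, not a TEAE.
- If the day is missing too, rule 3b gives 15 January 2023, still 334 days before the dose.

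**Do rules 4 and 5 help?** Rule 4 does not apply, because the month is recorded. Rule 5 needs a stop date before the imputed start or before the dose. An event that began after the dose also stops after it or is ongoing, and the imputed start is before the dose. Neither condition can be met.

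**Size of the misdating.** Let d be the days from dose to true start. In an assumed 2023 dose year the imputed start lies 365 - d days before the dose (366 - d for starts after 29 February 2024).
- Smallest: d = 180 with a January start (dose 5 July, start 1 January), 365 - 180 = 185 days.
- Largest: d = 1 (dose 31 December, start 1 January), 365 - 1 = 364 days. In a leap dose year it is 365.

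**All dose and onset combinations.** Dose dates from 5 July to 31 December give 1, 2, ..., 180 onset days in the next year: 180 × 181 / 2 = 16,290 pairs. Every one is dated before vaccination.

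**Which of these lose TEAE status?** A true TEAE needs d ≤ 29. A dose on 3 December reaches 1 January at d = 29, and a dose on 31 December reaches 29 January. That gives 1 + 2 + ... + 29 = 29 × 30 / 2 = 435 pairs, or 435 / 16,290 = 2.7%. The other 15,855 are outside the TEAE window even when dated correctly. For example, with a dose on 15 December 2023 and a start on 10 May, the true Onset is 148 and the imputed Onset is -218.

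**Calendar days exposed, by assumed dose date:**

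| Dose (2023) | Of the 30 TEAE days | Of days 0 to 180 |
|---|---|---|
| 15 November | 0 | 134 (74%) |
| 1 December | 0 | 150 (83%) |
| 15 December | 13 (43%) | 164 (91%) |

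These are shares of calendar days on which an event with no recorded year would be misdated. They are not shares of events.

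**The case against.** The strongest objection is that the trigger is remote. Protocol 8.5.2 asks for a start and stop date for every AE. Contacts at Day 8, Day 15, Month 1 and then monthly bound the year. SAEs are reported within 24 hours of awareness, and data are cleaned before each lock (SAP 2.6). A record that keeps its month and lacks its year at lock should be rare. Year-end exposure is also an assumption: a charter date is not a vaccination date, Stage 1 is 64 of about 1000 subjects, and doses from January to June cannot cross a year end within 180 days. All of this stands. It limits the size of the effect but does not make the rule correct.

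A reader might also infer more than the documents support.
- *That any January-to-June event loses TEAE status.* It does not. After 29 January no event following a December dose can be a TEAE.
- *That every start date without a year is affected.* With the month also missing, 3a uses the dose month. A completely missing date goes to rule 4.
- *That SAE, NOCI and MAAE events drop out of the 6-month percentages.* SAP 6.5.1.2 lists those tables with no onset filter. Protocol 10.6.3 does say that unsolicited AEs are selected and assigned to intervals by day of onset, so the loss is possible, but the SAP does not carry this over to those tables.
- *That rule 3 contradicts rules 4 and 5.* They address different cases, and the second part of rule 5 itself resolves to not treatment emergent.

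**Conclusion.** Rule 3 is wrong as written for one kind of record: month known, year missing, and true onset in the calendar year after the dose. Such an event is dated 185 to 364 days before vaccination (up to 365 in a leap dose year), and no other rule corrects it. TEAE status is wrongly lost only for doses on 3 to 31 December with onset on 1 to 29 January. For later onsets the consequence is a pre-vaccination date, with possible misclassification for the 6-month endpoints if onset date selects the events. The conclusion about the rule follows from its text and the calendar. Its practical effect depends on vaccination dates and on the number of such records, neither of which is stated, and is probably very small. This is a minor correction.

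**What to change.** Amend rule 3 to read:

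> If year is missing and month is known, impute the year that places the start date between informed consent and the end of the subject's study participation, consistent with the stop date. If more than one year or none fits, treat the AE as treatment emergent unless the stop date is before the first dose. Then impute a missing day by rule 1b, 2b or 2c. If month is also missing, keep 3a and 3b.

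Protocol 4.3 caps an individual's participation at 210 days, well short of a year, so normally at most one year fits. A month that resolves to before the dose month needs no day, since the event is then pre-dose whatever the day.

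A simpler rule, taking the earliest year that puts the start on or after the dose, should be avoided. SAEs are collected from consent. With a dose on 15 December 2023, an ongoing SAE that began on 1 December 2023 and was recorded without a year would move to 1 December 2024. That is 352 days after the dose (Onset 353), beyond the 180-day follow-up. The wording above keeps it at 1 December 2023.

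The cost is a few lines of SAP text and a small change to the date derivation, which also needs the consent and end-of-participation dates. No new data are required.

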6.3. Study Population

6.3.1. Subject Disposition

Subject disposition will be presented on the Screened Population by treatment group, by age group and overall, including the number screened, the number of screen failures, the number randomized and the number who received study vaccine administration. The study disposition will also be presented along with the reasons for early study withdrawal.

The summary will be repeated on the Exposed Population.

The number of subjects in the RND will be presented on the Randomized Population by treatment group, by age group and overall.

The number of subjects in EXP, SAF and IEP will be presented on the Exposed Population by treatment group, by age group and overall.

The following by-subject listings will be presented.

- Study completion information, including the reason for premature study withdrawal
- Visit dates
- Inclusion in study Analysis Sets
- Reason for exclusion from the IEP
- Protocol deviations

6.3.2. Demographic and Baseline Characteristics

Demographic and baseline characteristics will be presented. Summary will include the following: age, sex, ethnicity, race, height, weight, body mass index.

Medical history will be coded using Medical Dictionary for Regulatory Activities (MedDRA) and summarized alphabetically by System Organ Class (SOC) and Preferred Term (PT).

Childbearing potential and method of contraception will be presented in Listings only.

Table summaries to be produced by treatment group and overall and repeated for the following:

Populations: RND, SAF, IEP

Subgroups: Overall (50+), 50-59, 60+, 65+

Demographic, baseline characteristics and medical history data will also be provided in data listings on the Randomized Population.

6.3.3. Prior and Concomitant Medication

Prior and concomitant medications will be coded using the WHO Drug dictionary.

Prior medications will be defined as any medications with a start date before the date of study vaccine administration.

Concomitant medications will be defined as any medications with a start date on or after the date of study vaccine administration, as well as medications taken prior to the study vaccine administration and continuing after.

If a medication date or time is missing, or partially missing, and it cannot be determined whether it was taken on or after start of treatment, it will be considered a concomitant medication.

Results will be tabulated by Anatomic Therapeutic Class level 2 and preferred term.

Table summaries to be produced by treatment group and overall and repeated for the following:

Population: SAF

Subgroups: Overall (50+)

Prior and concomitant medications will be included in a by-subject data listings.

6.3.4. Exposure and Compliance

Frequency and percentage of subjects with vaccinations will be summarized. For subjects who received a vaccine, the administered vaccine will be summarized.

Table summary to be produced by treatment group and repeated for the following:

Population: RND

Subgroups: Overall (50+), 50-59, 60+, 65+

6.4. Efficacy Evaluation

Not Applicable.

6.5. Safety Evaluations

All Safety summaries to be produced by treatment group, for the following:

Population: SAF

Subgroups: Overall (50+), 50-59, 60+, 65+

6.5.1. Adverse Events

6.5.1.1. Solicited Adverse Events

Solicited AEs are protocol-specified local and systemic symptoms/events that are proactively collected from the subject and evaluated by the Investigator or designee. Solicited AEs are collected for 7 days after each injection, starting on Day 1, within an electronic diary.

Solicited AEs for this study are:

- Local events: Pain, Erythema (redness) at the injection site, Edema (swelling) at the injection site
- Systemic events: Fever (oral temperature $\geq 100.4^{\circ}\text{F}$), Fatigue, Headache, Muscle pain, Joint pain

The Subject and the Investigator will grade all AEs for severity from “mild” (grade 1) to “potentially life-threatening” (grade 4), except for severity of redness and swelling recorded as diameters (cm) and graded accordingly (see Guidance for Industry Toxicity Grading Scale for Healthy Adult and Adolescent Volunteers Enrolled in Preventive Vaccine Clinical Trials, September 2007 for details on grading scale).

Only Solicited AEs collected in the eDiary CRF, within 7 days after vaccine administration (i.e. from Day 1 to Day 7) will be analyzed in this Section. Solicited AEs continuing beyond 7 days after injection will be combined with unsolicited AEs and described separately as specified in Section 6.5.1.3.

Occurrence of a solicited AE on a specific Day will be identified by a Grade ≥ 1 for that AE on that day. Subject with no recorded grade on a specific day will be considered missing for that

day in the by-day summaries. For overall summaries (i.e. Solicited AEs within 7 days post-injection), only non-missing grades are considered to derive endpoints, i.e. a subject will be considered missing in these summaries, only if their grade is missing for all 7 days.

The following endpoints will be calculated:

- **Maximum severity (Investigator):**

For each solicited AE collected for a subject, the maximum severity will be the highest grade recorded, as per Investigator, for all occurrences of this AE within 7 days of vaccine administration (i.e., from Day 1 post-administration to Day 7) for the overall summary, or within a single day for the summary by day. There will be no replacement in case of missing severity.

- **Maximum relationship (Investigator):**

For each unsolicited AE collected for a subject, the maximum relationship will be the strongest relationship, as per Investigator, for all occurrences of this AE. There will be no replacement in case of missing relationship.

- **Time of first onset of first event (days):**

Day of onset of the first solicited AE, as per the nominal visit where the first solicited AE was first reported. This will range from 1 (Day 1 = Day of study vaccine administration) to 7 (Day 7).

- **Duration of solicited AEs (days):**

Number of days between the onset of the solicited AE (i.e. nominal visit of first occurrence of Grade \geq 1) and the end of the solicited AE (i.e. nominal visit when Grade is back to 0). If there are different occurrences of a same solicited AE within 7 days, the durations will be added up. For solicited AEs continuing beyond 7 days, the end day of the continuing unsolicited adverse event will be used as the end day for the calculation. If the unsolicited AE is ongoing (i.e. stop date is missing), then duration will be the Number of days between the onset of the solicited AE and the study discontinuation date.

Example 1: If a subject has a solicited event Pain starting on Day 1 and finishing on Day 4, the duration is 4.

Example 2: If a subject has a solicited event Fatigue starting on Day 2 and finishing on Day 3. And a new solicited event Fatigue starting on Day 7 and ending on Day 9. The Duration will be 2+3=5.

Frequencies and percentages of subjects experiencing each solicited AE will be presented overall and by severity. For each of the time points or time intervals presented in the summaries, only subjects with at least one observation (ie, any non-missing values but excluding "Not done/unknown") for the solicited AEs will be summarized.

The following summaries of subjects will be performed:

- Solicited AEs within 7 days post-injection, for each event and for any event, overall and by maximum severity. Details by category (local, systemic) will also be presented. (Severity as per Investigator)
- Possibly or probably related solicited AEs within 7 days post-injection, for each event and for any event, by maximum severity (Severity and Relatedness as per Investigator) This summary will only be presented on the Overall (50+) population.
- Not related solicited AEs within 7 days post-injection, for each event and for any event, by maximum severity (Severity and Relatedness as per Investigator) This summary will only be presented on the Overall (50+) population.
- Solicited AEs by day post-injection, for each event and for any event, overall and by maximum severity on that day. (Severity as per Investigator)
- Solicited AEs by day post-injection, for each event and for any event, overall and by maximum severity on that day. (Severity as per Subject)
- Time of first onset of solicited AEs within 7 days post-injection for each event and any event. Duration of solicited AEs, after injection, for each event. Maximum duration of any event. (Severity as per Investigator)

Listings of all solicited AEs will be provided by subject.

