### **6.11   Solicited Adverse Events**

Solicited AE will be collected for 7 days after vaccine administration, starting on Day 1. Solicited AE for this study are local events of pain, erythema (redness) and edema (swelling) at the injection site, and systemic events of oral temperature  $\geq 100.4^{\circ}\text{F}$ , fatigue, headache, muscle pain, and joint pain.

Subjects will be trained to complete an electronic diary (eDiary) via Zelta's electronic Patient Reported Outcomes (ePRO) system. The eDiary collects the primary safety endpoint data. This system is accessed via a secure URL and will be used to observe, measure, and record these solicited AE. A digital thermometer will be provided to the subject to measure oral temperature each day, and it is to be recorded daily in the diary. To record injection site local reaction, a ruler will be provided to the subject to measure the diameter of redness and swelling at the largest point of the reaction each day; it is to be recorded daily in the diary. Study staff will be provided with a Reference Guide for instructing subjects on accessing the Zelta ePRO system. Each user will be provided with login credentials and a temporary password. The Zelta ePRO system is web-based and accessed via a secure URL.

Study staff will review the signs and symptoms recorded in the diary and the action taken for the event during the subject's clinic visit. The electronic diary will serve as the primary source document and data will be automatically integrated into the subject visit Solicited AE form in the EDC platform for site staff view-only access. The Investigator will then assess all recorded solicited events for severity and relatedness. Severity will be graded according to the FDA Toxicity Grading Scale ([FDA, 2007](#)). The results of the Investigator's assessment, if different from the subject's entry, will be recorded in a separate eCRF specified for Investigators. For solicited injection site reactions, the relationship to study vaccine will be automatically recorded to be probably related, however, the Investigator will determine the relationship for each systemic solicited reaction.

Symptoms continuing beyond the solicited AE collection period (7 days following injection) will be collected and recorded as unsolicited AE in the source document. The start date of unsolicited AE will be equal to the date of onset of the solicited AE.

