## **9.3 Electronic Patient Reported Outcome Data**

This study will employ electronic transfers of external eDiary data generated from the subjects recording of solicited AE and actions taken for 7 days post-vaccination within a validated system that is 21 CFR Part 11 compliant. The eDiary is integrated into the EDC (Zelta) system and subject-reported outcome data are available as soon as the subject submits data. The eDiary is considered source documentation and should be limited to the subject's recording. The Investigator is responsible for the adequacy and accuracy of data associated with severity and relationship to study vaccine, and this is recorded on a separate source document from the eDiary.

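### Printed redness and swelling bins leave some diameters without a grade, and the SAP has no rule for an Investigator grade left blank because the raters agree

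*SAP*

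**What the plan says.** **Redness and swelling scale.** Protocol 10.6.2 takes these two reactions out of the Section 8.2 grading and bins them by largest diameter: Grade 0 for 0–2.4 cm, Grade 1 for >2.5–5.0 cm, Grade 2 for >5.1–10.0 cm and Grade 3 for >10.0 cm. Protocol 6.11 grades solicited events by the FDA toxicity scale. SAP 6.5.1.1 sends the reader to the same guidance for diameters. SAP section 7 states that nothing differs from the protocol's analyses.

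**Severity.** SAP 6.5.1.1 defines the 7-day endpoint so that "the maximum severity will be the highest grade recorded, as per Investigator, for all occurrences of this AE within 7 days of vaccine administration", and adds: "There will be no replacement in case of missing severity". Protocol 6.11 says that the results of the Investigator's assessment, "if different from the subject's entry, will be recorded in a separate eCRF specified for Investigators". Protocol 9.3 says of the diary: "The eDiary is considered source documentation and should be limited to the subject's recording". On the Investigator's severity and relationship data it says that "this is recorded on a separate source document from the eDiary", with no condition about disagreement.

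**Occurrence.** SAP 6.5.1.1 states: "Occurrence of a solicited AE on a specific Day will be identified by a Grade" of 1 or more. It names no rater there, nor in the rule that a subject is missing from the 7-day summaries only when all seven daily grades are missing. It limits the section with "Only Solicited AEs collected in the eDiary CRF", and protocol 6.11 states: "The eDiary collects the primary safety endpoint data".

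**The concern.** The first two primary endpoints are percentages of subjects reporting solicited local and systemic reactions, also broken down by maximum severity. Redness and swelling are two of the three local reactions. A scale with holes cannot classify every reading, and the lower hole lies on the boundary between having and not having the reaction. With two sources named for the scale and no declared change, a programmer has to choose between them.

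The severity breakdown has a smaller gap. If the Investigator's grade is stored only on disagreement, and a missing grade is never replaced, then the commonest case, agreement, has no stated value. These derivations should be settled in the plan rather than in code.

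**Working it through.** **Redness and swelling**

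1. Inputs, from protocol 10.6.2, as intervals in cm: Grade 0 = [0, 2.4]; Grade 1 = (2.5, 5.0]; Grade 2 = (5.1, 10.0]; Grade 3 = (10.0, ∞).
2. Values from 0 upward that fall in none of these: (2.4, 2.5] and (5.0, 5.1]. Each is 0.1 cm wide. There is no gap at 10.0 cm.
3. The documents do not state the reading resolution. At 0.1 cm steps the ungraded readings are 2.5 and 5.1 cm; at 0.5 cm steps, only 2.5 cm; at 1 cm steps, none.
4. Consequence if a reading is assigned to a neighbouring grade. At 2.5 cm the neighbours are Grades 0 and 1, so the choice decides whether the occurrence rule is met. At 5.1 cm they are Grades 1 and 2, so only severity changes.
5. Consequence if a reading is left ungraded. The SAP treats that day as missing and keeps the subject in the 7-day summary if any other day has a grade. A subject with one ungraded day and Grade 0 on the rest would then count as having no reaction, by default rather than by decision.
6. Size per reclassified subject. Arm sizes assume an even four-way split of 1000 (age 50+), 600 (50–59), 200 + 200 = 400 (60+) and 200 (65+), using the synopsis age targets. This gives 250, 150, 100 and 50 per arm, so one subject is worth 100/250 = 0.4, 100/150 = 0.67, 100/100 = 1.0 and 100/50 = 2.0 percentage points.
7. The separate redness and swelling rows carry this effect. The any-local percentage is less exposed, because a subject who also reports pain counts anyway, and protocol 2.1 gives pain as about 70% in PCV20 recipients.

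**Investigator grade**

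8. Taken together:
   - SAP 6.5.1.1 analyses the Investigator's grade and does not replace a missing one.
   - Protocol 6.11 can be read as entering that grade only when it differs from the diary.
   - Protocol 9.3 keeps the Investigator's grade out of the diary.
   - Neither document says what value is analysed when the raters agree.
   
   Applied literally, agreement gives no separate entry, hence a missing grade that is not replaced.
9. Illustration for pain: 250 × 0.70 = 175 reporters per arm. The share with a differing grade is not stated; assume 2% to 20%. The literal rule would leave 175 × 0.02 = 3.5 to 175 × 0.20 = 35 of the 175 in the severity breakdown. This is not a forecast. It shows that the literal rule cannot be what was meant.
10. Occurrence: the restriction to diary data and the statement that the diary collects the primary safety data both point to the subject's entry.

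**The case against.** **On the bins.** The gaps are 0.1 cm wide and look like a slip of notation. With coarse reading no subject is affected, and the SAP, which governs the programming, uses the guidance scale. Much of this is fair as to size. But the printed protocol rule still gives a 2.5 cm reading no grade, and a SAP that declares no change does not displace it. A reader might infer that the guidance cut-points differ from those in 10.6.2. The documents do not reproduce the guidance, so that cannot be shown. What stands is that two sources are named and one is incomplete.

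**On severity.** A reader might infer a definite conflict between SAP and protocol. The documents do not support that. Protocol 6.11 has the Investigator assess every recorded solicited event, protocol 7.1.3 schedules this at Day 8, protocol 8.2 and 8.5.2 require severity for all AEs, and SAP 6.5.1.1 says both raters grade. The Investigator must also judge relatedness for each systemic reaction, so that record cannot consist only of disagreements. A blank can fairly be read as agreement, in which case using the diary grade replaces nothing. The eCRF completion guidelines that might settle this are not among the documents. What stands is that the plan never states this reading.

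**On incidence.** A reader might infer that an Investigator's regrade to 0 removes a reported reaction from the primary percentages. The diary restriction and endpoints defined by what subjects report favour the diary, and the table tags attach the Investigator to severity, not to occurrence. The unnamed rater is missing detail.

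**On traceability.** A reader might also infer that the Month 1 outputs would hide the rule used. SAP 6.5.1.1 plans the by-day table once by Investigator and once by subject severity, and comparing the two could reveal it. SAP 2.6 leaves the Month 1 list of outputs to a separate document.

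**Conclusion.** The point holds in a limited form. The printed bins are wrong as written: two ranges of diameter have no grade, one of them on the line between absent and present in a primary endpoint, and the protocol and SAP do not point to one scale. The effect is 0.4 to 2.0 points per affected subject, depending on age group, under even allocation. How many subjects would be affected depends on reading resolution and on how many diameters fall in the gaps, neither of which the documents give. It is worth correcting because it touches the classification of primary-endpoint reactions and costs little.

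The missing rule for agreed Investigator grades is minor. The likely intent is clear and the diary is the natural basis for occurrence, but the no-replacement sentence should not be left to contradict that intent.

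**What to change.** 1. Reconcile protocol 6.11, 8.2 and 10.6.2 with SAP 6.5.1.1 to one contiguous redness and swelling scale in which every diameter has exactly one grade. The sponsor should confirm the cut-points. If the result differs from protocol 10.6.2, record that in SAP section 7.
2. In SAP 6.5.1.1, state that the analysed Investigator grade is the recorded one and otherwise the diary grade, and that this is not replacement of missing data.
3. In the same section, state that the Grade ≥1 occurrence rule and the rule on seven missing daily grades both use the diary entry.

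Cost: a few sentences in the SAP and a wording correction in the protocol, made before the interim database lock. No new data and no additional tables are needed.
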